IRB Submission AAAR4891

Version 06/10/19

Title: The effect of vaginal preparation with chlorhexidine gluconate vs. povidine-iodine vs. saline on vaginal bacterial colony counts in pregnant women

Study Purpose and Rationale

Cesarean delivery is the most common major surgical procedure performed in the United States, with one in three babies delivered by cesarean. Women who deliver by cesarean are 5 to 20 times more likely to develop postpartum endometritis than women who deliver vaginally.

Those women who labor prior to cesarean delivery are at greatest risk of infectious complications. Although the use of prophylactic systemic antibiotics prior to cesarean has significantly reduced the risk of endometritis, over 10% of women who undergo cesarean after the onset of labor will develop postpartum endometritis [1, 2]. These infections may lead to extended intravenous antibiotic therapy for new mothers, prolonged hospital length of stay, and increased health care expenditures [3].

At present, preoperative abdominal skin antisepsis and systemic antibiotic prophylaxis are routinely adopted strategies to reduce postoperative infectious complications. Multiple studies have also examined the effect of vaginal preparation (or washing) with povidine-iodine prior to cesarean delivery on postpartum endometritis and infectious complications. A 2014 Cochrane review of seven trials randomizing over 2500 women found that vaginal preparation immediately prior to cesarean significantly reduces the rate of post-cesarean endometritis from 8.3% in the control group to 4.3% in the vaginal preparation group (RR 0.45, 95% CI 0.25-0.81) with even greater effects observed in a smaller subset of women with ruptured membranes [4]. A review of evidence-based practices for cesarean delivery recommended vaginal preparation with iodine-base solution at the time of cesarean with a USPSTF grade of B (moderate certainty that the net benefit was moderate to substantial) [5]. Likewise, a 2015 review of evidence-based practices to reduce surgical site infections after cesarean delivery published in Infection Control & Hospital Epidemiology included preoperative vaginal cleansing among six interventions reviewed in good-quality articles with "strong" strength of evidence for effectiveness [6]. And finally, a recently published meta-analysis of pre-cesarean vaginal cleansing, which included sixteen trials of nearly 5,000 women, also found a significant reduction in endometritis with vaginal cleansing compared to placebo (RR 0.52, 95% CI 0.37-0.72). The authors concluded that preoperative vaginal cleansing with povidone-iodine 10% should be performed prior to all cesarean deliveries in women in labor and with ruptured membranes [7].

Despite this evidence, vaginal preparation immediate prior to cesarean delivery is not widely practiced. Among 167 maternal-fetal medicine fellows who responded

to a survey of preferred techniques at cesarean delivery in 2012, only 5% included pre-operative vaginal preparation among their preferences [8].

In addition to increasing acceptance of this practice, questions remain about the best antiseptic agent for reducing microbes in the vaginal mucosa. Although the majority of studies published on vaginal preparation at the time of cesarean have used povidone-iodine solutions, there is evidence that chlorhexidine preparations may be superior antiseptics. A recent randomized controlled trial published in the New England Journal of Medicine found that chlorhexidine-alcohol was superior to iodine-alcohol abdominal preparations at the time of cesarean for reducing the risk of surgical-site infections [9]. Furthermore, povidine iodine is contraindicated in patients with severe iodine allergy and its antiseptic properties may be affected by both vaginal pH and the presence of blood [10].

There is one published randomized control trial that compared povidone iodine to chlorhexidine for vaginal antiseptis prior to vaginal hysterectomy. Unlike vaginal preparation at the time of cesarean delivery, vaginal antiseptic preparation prior to hysterectomy in gynecological surgical is standard of care. This study showed that chlorhexidine solution was more effective than povidone iodine at reducing bacteria colony counts in the operative field [11].

Current practices

Vaginal preparation or washing in women undergoing cesarean who are not laboring or have rupture of membranes is not standard of care or indicated by current evidence. A vulvar and perineal wash with povidine-iodine solution is routinely performed immediately prior to all vaginal deliveries at our institution; however, this is not evidence-based or protocolized. In addition, vaginal preparation with povidine-iodine (or chlorhexidine, according to surgeon preference) is standard of care prior to vaginal procedures in pregnant and postpartum women such as cervical cerclage, chorionic villus sampling, or dilation and curettage for postpartum hemorrhage.

Pre-cesarean vaginal preparation is strongly supported by the current evidence discussed above to reduce rates of post-operative endometritis in women in labor or with ruptured membranes prior to cesarean. This is standard of care at certain institutions, and recently has been made standard of care at CHONY by instituting a new Perinatal Practice Guideline; however, because this is a relatively new initiative implementation may not yet be 100%.

Purpose

The purpose of this study is to see whether chlorhexidine is superior to povidine-iodine vaginal antisepsis at reducing bacteria colony counts in women undergoing cesarean by comparing three groups: vaginal washing with chlorhexidine, vaginal washing with povidine-iodine, and vaginal washing with saline alone.

Study design

This is a prospective trial of vaginal preparation (or vaginal cleansing/washing) on pregnancies admitted to CHONY Labor & Delivery unit for cesarean delivery *with three arms*. Randomization allocation would be performed in 1:1:1 fashion for vaginal preparation with chlorhexidine gluconate, povidine-iodine, and saline washes. A saline wash group is included to determine if the act of cleansing the vagina with a sponge alone reduces bacterial colony counts.

Primary outcome

- Aerobic and anaerobic post-preparaton vaginal bacterial colony counts in each group

Secondary outcomes

- Baseline aerobic and anaerobic vaginal bacterial colony counts
- Change in aerobic and anaerobic bacterial colony counts within each group
- Clinical infectious outcomes (although this study is not powered to detect these differences)

Inclusion criteria (intervention groups)

- Pregnant women admitted for cesarean delivery
- Gestational age \geq 34 weeks
- Maternal age greater than or equal to 18 years

Exclusion criteria (intervention groups)

- Rupture of membranes or active labor
- Chorioamnionitis (prior to enrollment)
- Recent (within 4 weeks) antibiotic exposure
- Maternal HIV infection or other known immunocompromised state
- Placenta previa or accreta
- Known allergy to shellfish or iodine
- Known allergy to chlorhexidine gluconate

Sampling (for the intervention groups these procedures will be performed in the operating room after anesthesia is placed)

- Three vaginal swabs of posterior fornix (aerobic culture, anaerobic culture, and quantitative PCR) taken immediately prior to vaginal preparation using sterile technique (this will be the only step for the laboring group).
- Vaginal preparation or wash performed over 30 seconds with three sponge sticks soaked in 1) low concentration chlorhexidine gluconate 0.5% solution; 2) povidine-iodine 10%; or 3) saline, according to randomization allocation.
- Additional three vaginal swabs of posterior fornix taken at 5-15 minutes after vaginal preparation is completed using sterile technique

Solution preparation

- A chlorhexidine gluconate 0.5% solution will be prepared by combining chlorhexidine gluconate 4% solution (1 part) with normal saline, i.e. sodium chloride 0.9% (7 parts).
- Povidine-iodine 10% and normal saline will be used directly as the products listed in the drugs/biologics section of the RASCAL IRB submission.

Data collection

- Baseline maternal demographic and pregnancy information will be collected at the time of sample collection (after consent is obtained) by abstraction from the electronic medical record
- Retrospective chart review of maternal and neonatal infectious outcomes at the time of discharge and at the time of the postpartum visit.

Statistical procedures and sample size

To our knowledge, this is the first study to assess vaginal bacterial counts in pregnant women after an antiseptic preparation. Therefore, we have selected a sample size of 10 women in each group for this pilot study.

Due to recent research that has shown race and ethnic-related differences in the vaginal microbiome of reproductive-aged and pregnant women [12, 13], our study will include equal numbers of Hispanic and African American women in each group.

The difference in change in CFUs pre and post intervention will be compared between groups.

Potential risks/benefits/alternatives

Risks:

The greatest risk of participating in the study is experiencing an allergic reaction or localized reaction/irritation to the solution used.

1) Chlorhexidine arm:

Chlorhexidine gluconate solution has an overall low rate of adverse or allergic reactions. All women undergoing non-emergent cesarean delivery at our institution receive abdominal preparation with chlorhexidine-alcohol (unless there is a known allergy) consistent with current evidence of its effectiveness and safety [9].

Chlorhexidine gluconate is not FDA-approved for use on mucosal surfaces.

However, chlorhexidine with low concentrations of alcohol (4% or less) are safe and effective for vaginal use. The off-label use of chlorhexidine solutions for vaginal preparation is supported by the American College of Obstetricians and Gynecologists in the setting of iodine allergy or surgeon preference [14]. At our institution, chlorhexidine vaginal preparation is routinely used at the time of gynecologic surgery according to surgeon preference. In addition, chlorhexidine-based mouthwashes are approved for use on oral mucosal surfaces in the treatment of gingivitis and periodontitis.

Of note, there is an FDA warning from February 2017 of rare but serious allergic reactions to *skin* antisepsis with chlorhexidine gluconate. However, this has not to our knowledge been reported with vaginal preparation, which generally uses a much lower concentration of chlorhexidine. There have been numerous large prospective published studies on chlorhexidine vaginal washing or irrigation in thousands of laboring pregnant patients (these studies had different research aims and therefore are not included under the study purpose and rationale) with no reported adverse effects [15-19].

2) Povidine-iodine arm

Povidine-iodine has an overall low rate of adverse or allergic reactions. In seven trials randomizing over 2800 women to povidine-iodine vaginal preparation prior to cesarean delivery, there were no reported side effects [4]. However, vaginal irritation or reaction is a possible side effect. All pregnant women undergoing vaginal procedures (such as chorionic villus sampling or cervical cerclage) receive vaginal preparation with povidine-iodine. In addition, it is routinely used in gynecologic procedures and surgery according to surgeon preference.

3) Saline arm

There is minimal risk with a vaginal saline wash. Localized irritation or minor discomfort may be possible due to sponge stick washing.

Finally, for all three arms, there is the potential risk of loss of confidentiality of sensitive health information, however this is unlikely. A code number will be used to separate data, biological samples, and health information from the participant's

name and other potential identifiers. The research file that links the code number to the patient's name will be kept in a locked cabinet, encrypted data file, or password-protected computer, and only the investigator and authorized study staff will have access to the file.

Benefits:

There are no personal or direct benefits from taking part in this study. However, the information collected from this research may help others in the future.

Alternatives:

Women may decline to participate in the study and undergo routine care on labor and delivery. Declining to participate will not impact their pregnancy, intrapartum or postpartum care.

Compensation:

The thirty participants undergoing vaginal preparation in the study will receive \$50 in cash for their time and effort.

References

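### The saline arm cannot isolate the effect of sponging, because no unsponged group is swabbed twice; its sound use is as the reference arm, in a between-arm comparison whose scale the plan should state

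*Combined protocol and SAP*

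**What the plan says.** All references are to the Combined protocol and SAP.

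- **Study design** gives the third arm its reason: "A saline wash group is included to determine if the act of cleansing the vagina with a sponge alone reduces bacterial colony counts".
- **Purpose** puts a different comparison first: "to see whether chlorhexidine is superior to povidine-iodine vaginal antisepsis at reducing bacteria colony counts".
- **Sampling** starts with "Three vaginal swabs of posterior fornix (aerobic culture, anaerobic culture, and quantitative PCR) taken immediately prior to vaginal preparation". For one further group, "this will be the only step for the laboring group".
- In the randomised arms the next step is "Vaginal preparation or wash performed over 30 seconds with three sponge sticks soaked in" one of the three fluids, followed by "Additional three vaginal swabs of posterior fornix taken at 5-15 minutes after vaginal preparation".
- **Primary outcome**: "Aerobic and anaerobic post-preparaton vaginal bacterial colony counts in each group". Among the **Secondary outcomes**: "Change in aerobic and anaerobic bacterial colony counts within each group".
- **Statistical procedures and sample size** sets 10 women per group as a pilot and has one sentence on analysis: the pre-to-post difference in colony-forming units is compared between groups. It names no scale, test, baseline adjustment or rule for cultures with no growth.

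**The concern.** To learn what sponging does, one needs women who are sampled at both times and not sponged. The plan has none. The three randomised arms differ only in the fluid. The laboring group has no second sample, and since active labor is an exclusion for the intervention arms, it is also a different population.

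The only evidence on sponging is therefore the saline arm's own before-after change. That change combines:

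- the sponge and the saline;
- material removed by three earlier swabs of the same site;
- the time up to the second swabs;
- any systemic antibiotic prophylaxis given between the two sets. Study Purpose and Rationale calls prophylaxis routine, and the plan does not give its timing relative to the swabs.

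A fall in the saline arm could be read as proof that sponging works, which this design cannot supply.

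What the saline arm can do is serve as the reference for each antiseptic. That use depends on the between-arm analysis, and there the plan leaves open whether change is taken on the raw or the log scale. With bacterial counts this choice decides whether a real difference can be seen.

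**Working it through.** **Plan's own figure.** 3 arms × 10 women = 30, which agrees with the thirty participants under Compensation. The 10 per group is a pilot choice with no power calculation to reproduce.

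**Assumptions.** The documents give no swab removal fraction, SD, test or detection limit. All values of these below are assumed.

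**1. Fall in the saline arm when the wash does nothing.** If each of three baseline swabs removes a fraction f, the fall is −3·log10(1−f). The 95% CI half-width for a mean change in 10 women is t(0.975, 9 df)/√10 × SD = 2.262/3.162 × SD = 0.715 × SD, that is 0.36, 0.72 and 1.07 log10 at SD 0.5, 1.0 and 1.5.

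| f per swab | Fall (log10) | Fall ÷ half-width, SD 0.5 | SD 1.0 | SD 1.5 |
|---|---|---|---|---|
| 5% | 0.07 | 19% | 9% | 6% |
| 10% | 0.14 | 38% | 19% | 13% |
| 20% | 0.29 | 81% | 41% | 27% |
| 30% | 0.46 | 130% | 65% | 43% |

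At 5% or less the bias is negligible. It matters mainly from about 20% with a small SD. From all non-sponge causes together, a fall of 0.25, 0.5 or 1.0 SD of the change would make a two-sided 5% paired test in the saline arm significant in 11%, 29% or 80% of trials with no sponge effect.

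**2. Contrasts between arms.** A removal factor (1−f)³ common to two arms adds the same constant to both log10 means and cancels in their difference. In simulation with a common non-sponge fall of 0, 0.5 or 1.0 SD, an antiseptic with no added effect differed significantly from saline in about 5% of trials each time.

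**3. Scale of the change.** Take a starting count of 1,000,000. A 2-log10 reduction leaves 10,000, a raw change of 990,000. A 1-log10 reduction leaves 100,000, a raw change of 900,000. The ratio is 0.99/0.90 = 1.10. A woman starting 1 log10 higher has a raw change ten times as large under either treatment, so raw change mostly reflects the starting count.

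Simulated trials: 10 per arm, log10 baseline normal with mean 6 and SD 1, true reductions of 2 and 1 log10, two-sided 5%. Percent of trials detecting the difference:

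| Analysis | SD of change 0.5 | 1.0 | 1.5 |
|---|---|---|---|
| Raw change, t-test | 1.5 | 1.9 | 1.4 |
| Raw post-wash count, t-test | 7 | 3 | 1 |
| Post-wash count, Mann-Whitney | 42 | 28 | 19 |
| Log10 post-wash, baseline-adjusted | 98 | 54 | 28 |

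Over baseline SDs of 0.5 to 1.5, raw change stays at 0.6-5.0% by t-test and about 4-10% by Mann-Whitney.

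**4. No-growth cultures.** In an assumed heavy-censoring case (reductions of 4 and 3 log10, SD of change 0.5, detection limit 100 CFU, no growth in 50% and 19%), the true difference is 1.0 log10. Baseline-adjusted estimates, with coverage of the nominal 95% CI:

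- no growth set to half the limit: 0.77, coverage 84%;
- no growth set to the limit: 0.68, coverage 70%;
- left-censored model: 1.00, coverage about 92%.

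**The case against.** Much of this is already in the plan. The Purpose compares three groups, the analysis sentence compares change between groups, and within-group change is only a secondary outcome. No section plans a test within the saline arm or a statement that sponging works. By a sponge alone the authors probably mean without antiseptic, so listing saline as a rival cause is partly a matter of words. Regression to the mean is unlikely to matter, because nobody is selected on baseline count, and the interval is short. All of this stands, and it reduces the first part to one verb that promises too much in a pilot.

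It also stands that the plan names neither scale nor test. Raw change is one possible reading, not a specified analysis, and the investigators may intend log10. A rank test on post-wash counts needs no transformation and does far better than raw change. A rank test on raw change does not rescue it, however, and no rank test in the table reaches the baseline-adjusted log10 model.

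A reader might infer that the missing control undermines the chlorhexidine versus povidone-iodine comparison, or that the saline arm is useless. The documents do not support either: those arms are randomised, identically sponged and swabbed on the same schedule, so shared influences cancel on the log10 scale. A reader might also infer that the laboring group could act as the unsponged control. It cannot, having one sampling time and a different population.

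**Conclusion.** The point holds as a minor overclaim plus an under-specified analysis. That the saline arm's change cannot be attributed to sponging follows from the documents alone. How far this would mislead cannot be known from them, and it may be very little. A paired analysis can still show whether counts fell; it cannot show why.

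The larger practical stake is the analysis sentence. If it were applied to raw counts, a true tenfold difference between arms would be detected in about 1-5% of trials by t-test or 4-10% by Mann-Whitney, against 98%, 54% or 28% for baseline-adjusted log10 counts at SD of change 0.5, 1.0 or 1.5. These figures rest on log-normal counts and assumed SDs. It would go too far to say that the plan has chosen raw counts, or that the study needs a fourth arm. The stated purpose can be met with the arms and swabs already planned.

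**What to change.** 1. **Reword the aim under Study design**: *The saline arm is the reference that controls for sponging, saline and repeat sampling, so that the effect of each antiseptic can be estimated.*
2. **Report the saline arm's before-after change as descriptive only**, in log10 CFU with a 95% CI. Label it the combined result of sponge, saline, repeat swabbing, elapsed time and any systemic antibiotic prophylaxis given between the swabs.
3. **Replace the analysis sentence under Statistical procedures and sample size**: *Post-wash log10 CFU will be compared between arms with adjustment for baseline log10 CFU, separately for aerobic and anaerobic counts: chlorhexidine versus povidone-iodine first, then each versus saline, as differences with 95% CIs. No-growth cultures will be treated as left-censored at the laboratory's detection limit (for example in a Tobit model), with a rank-based comparison as a sensitivity analysis.* This also brings the analysis into line with the primary outcome. Do not substitute the limit or half of it: in the example above both err in the same direction, so one is no check on the other.

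**Cost.** Only text and analysis change; no women, swabs or arm are added. The trial gives up a causal claim about sponging alone. Baseline adjustment spends one degree of freedom, which costs little (98.1% against 98.7% detection for log10 change at SD 0.5, when change does not depend on baseline). With 10 women per arm, intervals from a censored model are approximate: about 92% coverage in the assumed heavy-censoring case, short of the nominal 95%.

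### The labor exclusion is narrower than the group for whom the protocol calls vaginal preparation standard of care, so early labor with intact membranes is eligible as written (low priority)

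*Combined protocol and SAP*

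**What the plan says.** Under Exclusion criteria (intervention groups), the protocol removes women with "Rupture of membranes or active labor". It does not define active labor. The first inclusion criterion is "Pregnant women admitted for cesarean delivery"; the others set minimum gestational age (34 weeks) and maternal age (18 years). None requires a scheduled or pre-labor cesarean.

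Current practices says that the evidence supports preparation to reduce post-operative "endometritis in women in labor or with ruptured membranes prior to cesarean". It adds that the practice "recently has been made standard of care at CHONY by instituting a new Perinatal Practice Guideline", while allowing that uptake may be incomplete. The opening sentence of that section, beginning "Vaginal preparation or washing in women undergoing cesarean who are not laboring", describes the women for whom preparation is not standard.

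Study design sets 1:1:1 allocation to chlorhexidine, povidone-iodine or saline. In Sampling, the last step is "Additional three vaginal swabs of posterior fornix taken at 5-15 minutes after vaginal preparation is completed". Sampling also remarks that the pre-wash swab is the only step for a laboring group, which is defined nowhere else.

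**The concern.** A wash without antiseptic is easy to justify in women who would not otherwise receive preparation. The labor and membranes exclusion is the criterion that confines the saline arm to such women. Its membranes half matches the description of standard care, but its labor half carries a qualifier that the description lacks.

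The women left in the gap are those in early labor with intact membranes. As the text stands, such a woman could be allocated saline although the protocol elsewhere describes antiseptic preparation as standard for women in labor. The plan neither provides for nor forbids clinical preparation after the second set of swabs. The saline risk statement mentions only local irritation or minor discomfort, which suits a non-laboring population and does not address this woman.

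What is at stake is whether screening selects the women the authors meant to select. The comparison of colony counts between randomized arms is not in question.

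**Working it through.** **Step 1: set the texts side by side.**

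| Place in the protocol | Labor condition | Membranes condition |
|---|---|---|
| Current practices: preparation supported and now site standard | in labor, no stage named | ruptured |
| Exclusion criteria (intervention groups) | active labor only, undefined | ruptured |

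The two conditions are joined by *or* in both rows. Subtracting the second row from the first leaves women in labor that is not active, with intact membranes.

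**Step 2: look for another rule that closes the gap.** The three inclusion criteria do not, because any admission for cesarean qualifies. The remaining exclusions concern chorioamnionitis, recent antibiotics, immune status, placenta previa or accreta, and allergies. None refers to labor.

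**Step 3: check whether the background text uses the same qualifier.** Study Purpose and Rationale states the raised risk as "over 10% of women who undergo cesarean after the onset of labor will develop postpartum endometritis". That is background risk rather than a rule of care, but it too names no stage. In the passages compared here, the qualifier appears only in the exclusion.

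**Step 4: the plan's own numbers.** Statistical procedures and sample size gives 10 women per group. With three groups, 3 × 10 = 30, which agrees with the thirty participants under Compensation. The chance of saline for any eligible woman is 1/(1 + 1 + 1) = 10/30 = 0.333, or 1 in 3.

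**Step 5: how many women?** The documents do not say how many of the 30 might be in early labor, so the count *k* below is an assumption for illustration. The expected number given saline is *k*/3. With exactly 10 of 30 allocated to saline, the chance that at least one of the *k* receives it is 1 − C(20, *k*)/C(30, *k*).

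| Assumed *k* of 30 | Expected in saline arm | Chance of at least one in saline arm |
|---|---|---|
| 0 | 0 | 0% |
| 1 | 0.33 | 33% |
| 2 | 0.67 | 56% |
| 3 | 1.00 | 72% |
| 5 | 1.67 | 89% |

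For example, *k* = 2 gives 1 − 190/435 = 0.563. Nothing in the documents favors one row over another, and *k* = 0 is possible.

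**Step 6: after the change.** If labor at any stage is excluded and this is checked before allocation, a woman recognized as being in labor is not randomized, and her chance of a saline study wash falls from 1/3 to 0.

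**The case against.** The strongest reply is that laboring women were never meant to be washed. The eligibility lists are headed as applying to the intervention groups, and Sampling refers to a laboring group that has the first swabs and nothing more. That group may be a remnant of another design, but it is the best evidence of intent in the document, and the saline risk statement is consistent with it. This stands, and it is the main reason for the low priority. It does not remove the gap, because screening staff apply the written criterion and the laboring group is itself undefined.

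Second, Current practices is loosely worded. Its opening sentence, taken strictly, could be read as saying that preparation is not standard when membranes are ruptured, which conflicts with the later paragraph. If the section uses shorthand, *active labor* may be shorthand too. The site guideline is not in the documents and may define labor as active labor, in which case there would be no mismatch with it. One meta-analysis conclusion in Study Purpose and Rationale is also worded for labor *and* ruptured membranes, which is less clear for intact membranes. These points stand as uncertainty about how much the mismatch matters; the difference in wording remains.

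Third, a reader might infer that the trial withholds standard care. The documents do not support that. Nothing bars clinical preparation before, instead of or after the study wash, and the protocol itself notes that "because this is a relatively new initiative implementation may not yet be 100" percent, so preparation outside the trial is not assured either.

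Fourth, a reader might turn the review rates of 8.3% and 4.3% under Study Purpose and Rationale into an excess endometritis risk. That would apply rates from a whole review population to a subgroup for which the documents give no rate. It would also need assumptions about guideline uptake, any benefit from sponging with saline, and later clinical preparation. No such figure should be attached.

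**Conclusion.** The point holds as a wording gap. The exclusion is narrower than the population the protocol describes as receiving preparation as standard care, and no other criterion covers the difference. A woman in early labor with intact membranes is eligible as written and has a 1 in 3 chance of a saline study wash.

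This rests on a literal reading of *active* and on taking the description under Current practices at face value, with the site guideline unseen. The number of women affected is unknown and may be zero. Loss of standard care is possible but not established. The documents give no ground for inferring bias between arms or an analysis error from this point. Low priority, but worth correcting because the change is nearly free and brings the criterion into line with the apparent intent.

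**What to change.** Delete *active*, so that the criterion reads: *Rupture of membranes or labor (any stage)*. Confirm it just before the allocation is opened, since labor can begin between consent and the operating room. Naming every stage avoids tying the criterion to the guideline's definition: if the guideline meant active labor only, a cross-reference to it would leave the gap open.

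The cost is a one-line amendment and one brief eligibility check. A few women may become ineligible and recruitment may slow slightly. The planned total stays at 30.

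### Every bacterial-load outcome is a culture count from swabs taken minutes after the wash, and the plan requires no step to neutralise antiseptic left on those swabs

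*Combined protocol and SAP*

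**What the plan says.** The Sampling section takes three swabs just before the wash, one each for "aerobic culture, anaerobic culture, and quantitative PCR". After a wash with soaked sponge sticks it specifies: "Additional three vaginal swabs of posterior fornix taken at 5-15 minutes after vaginal preparation is completed using sterile technique". The types of the second set are not restated; the natural reading is the same three. This is the only place where PCR is mentioned. The same section refers to a laboring group that has the first set of swabs only.

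The primary outcome is "Aerobic and anaerobic post-preparaton vaginal bacterial colony counts in each group". The secondary outcomes are "Baseline aerobic and anaerobic vaginal bacterial colony counts", "Change in aerobic and anaerobic bacterial colony counts within each group", and clinical infection, for which the protocol says the study is not powered. The only analysis sentence, under Statistical procedures and sample size, is "The difference in change in CFUs pre and post intervention will be compared between groups".

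The protocol does not mention a neutralising agent, a rinse, a transport medium or any other control of antiseptic remaining on the swab.

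**The concern.** A colony count measures what grows on the plate. It reflects viable bacteria in the vagina only if nothing carried over with the specimen goes on inhibiting growth. The post-wash swabs come from a site that, in two of the three arms, was washed with antiseptic 5 to 15 minutes earlier. Any residue on the swab could lower the count after sampling. The saline arm has no antiseptic to carry over.

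This would be a measurement error caused by the assigned treatment, so randomisation does not balance it. The pre-wash swab is taken before any exposure, so subtracting it or adjusting for it does not help. A lower post-wash count in an antiseptic arm could then be killing in the vagina, suppressed growth on the plate, or both, and the data would not say which. Antiseptic versus saline is directly exposed. Chlorhexidine versus povidone-iodine, the comparison named under Purpose, is exposed only if the two agents carry over to different degrees.

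**Working it through.** **1. Sample size.** Statistical procedures and sample size gives 10 women per group, and Study design gives three arms at 1:1:1. 3 × 10 = 30, which agrees with the thirty washed participants under Compensation. The 10 per group cannot be derived further, because the plan states no alpha, power, effect size or SD.

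**2. What each swab feeds.**

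| Item in the plan | Measurement used |
|---|---|
| Primary outcome: post-wash counts | culture |
| Secondary: baseline counts | culture |
| Secondary: within-group change in counts | culture |
| Secondary: clinical infection (not powered) | chart review |
| Only stated analysis: between-group change in CFUs | culture |

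Culture supplies 3 of 3 bacterial-load outcomes and the 1 analysis. PCR supplies 0 of 3 and 0 of 1. For the washed women, 30 × 6 = 180 swabs, of which 30 × 2 = 60 (one third) are PCR swabs if the second set repeats the first. Women in the laboring group are not in this count.

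**3. Where carry-over enters.** Let *c* be the log10 reduction in the recovered count that is due only to residual antiseptic, with *c* = 0 for saline and *c* = 0 for every pre-wash swab.

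- Measured change in an arm = true change − *c*.
- Antiseptic minus saline = true difference − *c*.
- Chlorhexidine minus iodine = true difference − (*c* for chlorhexidine − *c* for iodine).

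The whole of *c* passes into the first contrast, whether the post-wash count or the change is analysed. In the second, only the difference between the agents remains, and it is zero if they carry over equally.

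**4. Illustration of size (all inputs assumed except 10 per arm).** Take a two-sample t-test at two-sided 5%, log10 counts, a common SD and no true difference. The degrees of freedom are 18, the critical value is 2.101, and the noncentrality is (*c*/SD) × √(10/2) = 2.236 × *c*/SD. Halving the recovered count gives *c* = log10(2) ≈ 0.3, and a tenfold loss gives *c* = 1.0.

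| Assumed SD (log10) | Rejection at *c* = 0.3 | Rejection at *c* = 1.0 |
|---|---|---|
| 0.7 | 15% | 86% |
| 1.0 | 9.7% | 56.2% |
| 1.5 | 7% | 29% |

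For SD 1.0 the noncentralities are 0.67 and 2.24. With *c* = 0 the rate is 5%. These figures are for one antiseptic-versus-saline test. They would apply to chlorhexidine versus iodine only with *c* replaced by the difference in carry-over.

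**5. What PCR could and could not show.** If bacteria are killed in the vagina, culture falls, and PCR may not, because it can detect DNA from dead bacteria. If growth is only suppressed on the plate, culture falls and PCR does not. Both explanations can produce the same pattern of low culture and unchanged PCR, so PCR does not separate them.

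**The case against.** The documents report no carry-over and give no figure for it. They contain no laboratory methods at all, and this is a short description that refers to another part of the IRB submission for product details. Silence on a neutraliser therefore does not show that none will be used. The protocol's stated reason for the saline arm is to see whether sponging alone lowers counts. Saline's own before-and-after change answers that with no antiseptic present. The named comparison, chlorhexidine versus iodine, is biased only if carry-over differs. The study calls itself a pilot with 10 per group, and every input to the error-rate illustration other than that 10 is assumed.

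Most of this stands as a limit on strength. Carry-over is a possibility, not a finding, and the percentages are not evidence about this trial. It does not remove the point. Antiseptic versus saline is still among the planned between-group comparisons. The plan as written does not protect its primary measurement, and neutralisation cannot be added once a swab has been taken. Pilot status is a weak defence, because a later trial would inherit the measurement method and any bias in it. If a laboratory procedure already covers neutralisation, one sentence citing it settles the matter.

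A reader might infer that the PCR swabs would expose carry-over and that leaving them out of the outcomes is the main fault. The documents do not support this, because culture and PCR can diverge in the same way under true killing and under suppressed growth. Nor do they show that the PCR specimens have no purpose: the assay is designated, and what is missing is an outcome and an analysis.

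**Conclusion.** The point holds as a cheap improvement. Followed as written, the plan leaves its primary culture outcome open to a bias that would act only in the two antiseptic arms. It would affect antiseptic versus saline by the full amount of carry-over, and chlorhexidine versus iodine by any difference between the agents. The amount is unknown. The rise from 5% to roughly 10% to 56% rests on an assumed carry-over of 0.3 to 1.0 log10, an assumed SD of 1.0 log10, a log-scale t-test and no true difference. It should not be read as this trial's error rate.

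Two wider readings should be avoided. The trial does not rely on culture for everything: clinical infectious outcomes are also listed, though unpowered. Sampling before and after the wash applies to the 30 washed women, not to the laboring group. The missing PCR outcome is a minor, separate gap.

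**What to change.** **Main change, in Sampling:** require that all culture swabs, before and after the wash and in all three arms, go into the same antiseptic-neutralising transport medium. Using it at both times and in every arm keeps the handling identical, so that the medium itself cannot create a difference between arms. The cost is a small amount for supplies. The number of women, the arms, the washes and the number of swabs do not change. It must be in place before sampling starts.

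**Supporting change, in Secondary outcomes:** for the 30 washed women, add log10 bacterial load by quantitative PCR after preparation, adjusted for the pre-preparation value. Label it a supportive measure of total load, viable plus non-viable, and do not present it as a check for carry-over. State that the post-wash set repeats the three swab types. The cost is a few lines of text, one analysis of specimens already planned, and one more secondary comparison.
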